Appendix I. RACD Individual questionnaire

1. Barcode: _____

This field should auto populate after Surveillance Agent clicks on 'Edit' button from RACD Household Level dashboard as barcode was already assigned.

2. Household ID: _____

This field should auto populate after Surveillance Agent clicks on 'Edit' button from RACD Household Level dashboard as Household ID was already assigned.

3. Consent obtained: Yes No Not yet

If no, trigger the Refuser Survey

Questionnaire will only be administered if household member is found at home. Auto-populate 'Not yet' option for consent obtained based on information collected from household level questionnaire. The 'Not yet' option must be greyed out (disabled) though showing that it was a previous selection option. Surveillance Agents must then either select 'Yes' or 'No', with the 'No' option triggering the refuser survey

4. Relation to index case (check all that apply):

Immediate Family Extended family Neighbor Visitor Co-worker Unknown

5. Nationality:

Swaziland Mozambique South Africa Other (specify _____)

(Provide drop down list of all nationalities)

6. Occupation (*Drop down list*):

Student Child or minor but not a student Unemployed
 Farming/Agriculture Manufacturing/Factory Other Manual Labor
 Small-market sales or trade Office or Clerical Work Other (specify _____)

7. Ask: Have you been diagnosed with malaria in the past 12 months? Yes No

If yes, ask when,

6 months to a year ago < 6 months ago Within the last month Within the last 2 weeks
 Don't know

If yes ask, have you had fever in the last 2 weeks? Yes No Don't know

If yes ask, have you been diagnosed with malaria in the last 2 weeks? Yes No Don't know

If diagnosed in the last 2 weeks:

Was the diagnosis confirmed by a test? Yes No Don't know

What treatment was prescribed? *Check all that apply*

Artemether-lumefantrine
 Single dose primaquine
 Oral Quinine
 IV Quinine
 IM Quinine
 IV Artesunate
 IM Artesunate
 Chloroquine
 SP/Fansidar
 Other (specify _____)
 Unknown

Was full treatment course completed? Yes No Don't know

Prior Residence and/or Travel History

8. Have you ever lived or stayed in Mozambique for at least 30 consecutive days?
If yes, approximately how long ago was this visit or stay? ___ yrs ___ mos

9. Have you spent at least one night anywhere else besides your current residence in the past 8 weeks?
 Yes No Don't know

- ***If no, skip to question 10.***

- *If yes, ask: Where did you sleep overnight, when did you sleep there, why did you sleep there, and personal protection? If slept outside Swaziland, also ask about means of travel and border post of re-entry.*

Within Swaziland				
Town / Locality / Inkhundla	Duration of Stay		Reason for sleeping away from current residence: -previous residence -business -holiday -visiting friends/family -other (specify, ____)	Personal protection -chemoprophylaxis (specify__) -bednet -mosquito repellent or coil -None
	First Night YY/MM/DD	Last Night YY/MM/DD		
a.				
b.				
c.				
d.				
e.				

Outside of Swaziland							
Country	Province / Town	Duration of Stay		Reason for sleeping away from current residence: -previous residence -business -holiday -visiting friends / family -other (specify____)	Personal protection -chemoprophylaxis (specify__) -bednet -mosquito repellent or coil -None	Means of travel -Large bus -Kombi (van) -Personal car -Ride share (catch a ride / got a lift) -Airplane -Bicycle -Walked -Other (specify____)	Border Post of Re-Entry - Lavumisa/Golela - Salitje/Onverwacht - Mahamba - Gege/Bothashoop - Sicunusa/Houtkop - Sandlane/Nerston - Ngwenya/Oshoek - Bulembu/Josefsdal - Matsamo/Jeppe's Reef - Mananga - Lomahasha/Namaacha - Mhlumeni/Goba - KMIII International Airport - Other
		First Night YY/MM/DD	Last Night YY/MM/DD				
a.							
b.							
c.							
d.							
e.							

10. *Comments or any other information that is relevant?*

11. RDT result: positive negative not done

If positive, patient referred to local health facility Yes No

If no, why? _____

DBS collected Yes No Not Done

If DBS not done, why? Patient refused Other _____

Thank you for our participation in this study.

Appendix J. Household level TPE questionnaire

Complete for all households (including households of the index case and households where no one is home or there is no consenting adult available). Note, in the event that this household has already previously participated in TPE, a new Household level TPE questionnaire should still be completed.

Neighborhood ID: _____

Automatically generated by the tablet based on index case GPS coordinates. If GPS coordinates within the same 200 m radius as previously implemented index case investigation then assign same Neighborhood ID. Make sure automated number is unique for all tablets.

Index case ID (aciid): _____

Surveillance Agent assigns barcode number to index case

Visit 1: Date: _____ (YY/MM/DD) Time of arrival: ____: ____ (hh:mm AM/PM)

Visit 2: Date: _____ (YY/MM/DD) Time of arrival: ____: ____ (hh:mm AM/PM)

Visit 3: Date: _____ (YY/MM/DD) Time of arrival: ____: ____ (hh:mm AM/PM)

For Visit 1, Date and Time captured automatically when household level questionnaire is saved. There should be 3 date fields, First Entered, Last Modified and Final Entered. On first visit same date is saved on all 3 fields.

For Visit 2, Last Modified and Final Entered should be modified to reflect that day's date and time, this should be done on the Individual level questionnaire and not the household level questionnaire unless edits were made to the household level questionnaire.

For Visit 3, Final entered should be modified to reflect that day's date and time, this should be done on the Individual level questionnaire and not the household level questionnaire unless edits were made to the household level questionnaire.

TPE Household Information

9. Household ID (automatically generated by tablet) _____

Automatically generated by tablet and should be unique for all tablets to prevent duplication

10. Household description (if household not a residential premise e.g. Church, describe here) _____

11. GPS Coordinates

Latitude: _____

Longitude: _____

Automatically captured by tablet when household level questionnaire is saved, allow functionality to edit GPS coordinates by Agents

12. Surveillance Agent Name, check all that apply

[name] [name] [name] [name] [name] [name] [name]
 [name] [name] [name] [name] [name] Other _____

13. Is household abandoned? Yes No

If Yes, continue to next question.

If No, close and save questionnaire.

14. Is a consenting adult available? Yes No

If Yes, continue to next question.

If No, please indicate number of household members if known ____ (based on neighbor report, otherwise default is "999") and skip to end of questionnaire and move to next home.

999 denotes unknown number of households members

15. Has this home been sprayed in the past year? Yes No Don't Know

If yes, ask to see spray card to confirm house has been sprayed.

Spray card confirmed
 No spray card
 Cannot find spray card

If yes, we're all the houses sprayed?

Yes No Don't Know

If yes, do you sleep under a sprayed structure?

Yes No Don't Know

16. Has this household previously participated in TPE before (during this TPE study period)?

Yes No Don't Know

If yes, how many times before? ____

If yes, indicate month(s) and year(s) of all previous TPE interventions during this TPE study period

1. _____ (dd/mm/yyyy)

2. _____ (dd/mm/yyyy)

3. _____ (dd/mm/yyyy)

8. List individuals in the household:

	Household head? (check if yes)	Index case? (check if yes)	Name	Scan Barcode	Gender	Date of birth	Present (yes/no)	Notes (why person not present at home and best time to return to speak with person)	Consent obtained for questionnaire (yes/no/not yet)
1.									
2.									
Etc.									

Note: Surveillance Agent to assign a barcode even if individual is not present

TPE Household level Dashboard (automatically generated)

	Barcode	Name	Household head? (check if yes)	Index case? (check if yes)	Gender	Age	Consent obtained for questionnaire (yes/no/not yet)	Questionnaire completed (yes/no)	Eligible for medication	Medication consent	# doses completed	Notes	
1.													Edit
2.													Edit
3.													Edit
													Add Individual

Editable table listing all household members rising in a household, when a Surveillance Agent clicks on the 'Edit' button they will be shown the questionnaire below to insert information on additional questions not previously posed. When TPE questionnaire for household member is completed the table should refresh and 'Yes' should appear under column for TPE Questionnaire completed and other fields that have since been completed.

TPE Neighborhood Dashboard (automatically generated and includes missed homes)

Note: Use outlined boxes for the "30" criteria

Household number	Home of the index case, check if yes	Name of Household head	# of individuals eligible for participation	# of individuals reached (informed consent performed)	# of individuals providing consent for questionnaire	# of questionnaires completed	# of individuals eligible and consented to receive medication	# of individuals received dose 1	# of individuals received dose 2	# of individuals received dose 3
Totals:										

Appendix K. TPE Individual questionnaire

1. Barcode: _____

This field should auto populate after Surveillance Agent clicks on 'Edit' button from TPE Household Level dashboard as barcode was already assigned.

2. Household ID: _____

This field should auto populate after Surveillance Agent clicks on 'Edit' button from TPE Household Level dashboard as Household ID was already assigned.

3. Consent obtained: Yes No Not yet

If no, trigger the Refuser Survey

Questionnaire will only be administered if household member is found at home. Auto-populate 'Not yet' option for consent obtained based on information collected from household level questionnaire. The 'Not yet' option must be greyed out (disabled) though showing that it was a previous selection option. Surveillance Agents must then either select 'Yes' or 'No', with the 'No' option triggering the refuser survey

4. Relation to index case (check all that apply):

Immediate Family Extended family Neighbor Visitor Co-worker Unknown

5. Nationality:

Swaziland Mozambique South Africa Other (specify _____)

(Provide drop down list of all nationalities)

6. Occupation (*Drop down list*):

Student Child or minor but not a student Unemployed
 Farming/Agriculture Manufacturing/Factory Other Manual Labor
 Small-market sales or trade Office or Clerical Work Other (specify _____)

7. Ask: Have you been diagnosed with malaria in the past 12 months? Yes No

If yes, ask when,

6 months to a year ago < 6 months ago Within the last month Within the last 2 weeks
 Don't know

If yes ask, have you had fever in the last 2 weeks? Yes No Don't know

If yes ask, have you been diagnosed with malaria in the last 2 weeks? Yes No Don't know

If diagnosed in the last 2 weeks:

Was the diagnosis confirmed by a test? Yes No Don't know

What treatment was prescribed? *Check all that apply*

Artemether-lumefantrine
 Single dose primaquine
 Oral Quinine
 IV Quinine
 IM Quinine
 IV Artesunate
 IM Artesunate
 Chloroquine
 SP/Fansidar
 Other (specify _____)
 Unknown

Was full treatment course completed? Yes No Don't know

Prior Residence and/or Travel History

12. Have you ever lived or stayed in Mozambique for at least 30 consecutive days?

If yes, approximately how long ago was this visit or stay? ___ yrs ___ mos

13. Have you spent at least one night anywhere else besides your current residence in the past 8 weeks?

Yes No Don't know

- ***If no, skip to question 10.***

- *If yes, ask: Where did you sleep overnight, when did you sleep there, why did you sleep there, and personal protection? If slept outside Swaziland, also ask about means of travel and border post of re-entry.*

Within Swaziland				
Town / Locality / Inkhundla	Duration of Stay		Reason for sleeping away from current residence: -previous residence -business -holiday -visiting friends/family -other (specify, _____)	Personal protection -chemoprophylaxis (specify___) -bednet -mosquito repellent or coil -None
	First Night YY/MM/DD	Last Night YY/MM/DD		
a.				
b.				
c.				
d.				
e.				

Outside of Swaziland							
Country	Province / Town	Duration of Stay		Reason for sleeping away from current residence: -previous residence -business -holiday -visiting friends/family - Other (specify_____)	Personal protection (specify___) -chemoprophylaxis -bednet -mosquito repellent or coil -None	Means of travel -Large bus -Kombi (van) -Personal car -Ride share (catch a ride/got a lift) -Airplane -Bicycle -Walked -Other (specify_____)	Border Post of Re-Entry - Lavumisa/Golela - Salitje/Onverwacht - Mahamba - Gege/Bothashoop - Sicunusa/Houtkop - Sandlane/Nerston - Ngwenya/Oshoek - Bulembu/Josefsdal - Matsamo/Jeppe's Reef - Mananga - Lomahasha/Namaacha - Mhlumeni/Goba - KMIII International Airport - Other
		First Night YY/MM/DD	Last Night YY/MM/DD				
a.							
b.							
c.							
d.							
e.							

Medical History

10. *Weight:* ___ . ___ kg

Tablet should make this question compulsory for all ages

Ask the following questions to assess for potential criteria excluding participant from receiving antimalarial medication:

11. Are you pregnant or breastfeeding? Yes No Don't know

12. Have you menstruated in the past but not within the past 4 weeks? Yes No Don't know

13. Are you less than 9 months of age? Yes No Don't know

Tablet should automatically complete this question based on date of birth, select an option and not allow Agent to make changes

14. Are you allergic to have had a past adverse reaction to DP? Yes No Don't know

15. Have you already taken 2 courses of DP in the past year? Yes No Don't know

16. Have you taken DP within the last 2 months? Yes No Don't know

17. Do you have heart, kidney, or liver problems? Yes No Don't know

18. Does your family have a history of heart problems or sudden death? Yes No Don't know

19. In the past month have you taken antimalarial drugs for either treatment or prevention of malaria (mefloquine, halofantrine, lumefantrine, chloroquine, or quinine)? Yes No Don't know

20. Have you had a fever in the past 48 hours, or are otherwise feeling ill? Yes No Don't know

If Yes, was subject taken to local health facility? Yes No

21. Are you currently taking any medications? Yes No Don't know

If Yes, are you taking any of the following medications? (check all that apply)

a. Medicines that effect heart rhythms (such as amiodarone, disopyramide, dofetilide, ibutilide, procainamide, quinidine, hydroquinidine, or sotalol)

b. Medicines that treat depression

c. Medicines that treat mental health problems (such as phenothiazines, sertindole, sultopride, chlorpromazine, haloperidol, mesoridazine, pimozone, or thioridazine)

d. Medicines that treat infection (macrolides [such as erythromycin or clarithromycin], fluoroquinolones [such as moxifloxacin or sparfloxacin], medicines for fungal infections [such as imidazole and fluconazole], as well as pentamidine [used to treat a specific type of pneumonia] and saquinavir [for treatment of HIV])

e. Antihistamines used to treat allergies or inflammation (such as terfenadine, astemizole, mizolastine)

f. Medicines that treat stomach problems such as cisapride, droperidol, domperidone, or diphemanil

g. Medicines to treat cancers (vinca alkaloids, arsenic trioxide), chest pain (bepridil), drug addiction (levomethadyl, methadone), and high cholesterol levels (probucole)

Drug Administration: (Subject is eligible to receive medication if they weigh at least 7kg and answered "No" to questions 10-19 and are not taking any of the medications listed in 20a-20g)

22. Is the subject eligible to receive medication? Yes No

Tablet to automatically say Yes or No for eligibility of individual to receive medication based on responses above and criteria provided, options should be greyed out (disabled).

a. *If yes, indicate regimen administered:*

Check one	Weight band	Color of box	Regimen administered	Subscription
	7-12 kg	Bottle	320 mg piperazine /40 mg dihydroartemisinin tablets, 3 half tablets	½ tablet daily x 3 days
	7-12 kg	Pink box	160 mg piperazine /20 mg dihydroartemisinin tablets, 3 tablets	1 tablet daily x 3 days
	13-23 kg	Green box	320 mg piperazine /40 mg dihydroartemisinin tablets, 3 tablets	1 tablet daily x 3 days
	24-35 kg	Orange box	320 mg piperazine /40 mg dihydroartemisinin tablets, 6 tablets	2 tablet daily x 3 days
	36-74 kg	Purple box	320 mg piperazine /40 mg dihydroartemisinin tablets, 9 tablets	3 tablet daily x 3 days

	> 74 kg	Blue bag	320 mg piperazine /40 mg dihydroartemisinin tablets, 12 tablets	4 tablet daily x 3 days
--------------------------	---------	----------	---	-------------------------

NOTE: Give lower weight band if weight falls between weight bands.

NOTE: Use of the 320/40 mg or 160/20 mg tablet for children 7-12 kg will depend on drug availability.

b. Was dose #1 directly observed? Yes No, indicate reason _____

23. Comments or any other information that is relevant?

24. Modified DOT record

Encounter #	Date YY/MM/DD	Time ##:## AM/PM	Oversight (check one)	Comments
1			 Dose #2 DOT by study staff  Dose #2 Self-reported self-administration  Dose #2 Self-administered (reported by someone other than the subject)  Dose #2 Reminded patient to take drug  Dose #2 Indirectly reminded patient to take drug (via close contact)  Dose #2 Other, specify _____	
2			 Dose #2 DOT by study staff  Dose #2 Self-reported self-administration  Dose #2 Self-administered (reported by someone other than the subject)  Dose #2 Reminded patient to take drug  Dose #2 Indirectly reminded patient to take drug (via close contact)  Dose #2 Other, specify _____ <hr/>  Dose #3 DOT by study staff  Dose #3 Self-reported self-administration  Dose #3 Self-administered (reported by someone other than the subject)  Dose #3 Reminded patient to take drug  Dose #3 Indirectly reminded patient to take drug (via close contact)  Dose #3 Other, specify _____	
3			 Dose #2 DOT by study staff  Dose #2 Self-reported self-administration  Dose #2 Self-administered (reported by someone other than the subject)  Dose #2 Reminded patient to take drug  Dose #2 Indirectly reminded patient to take drug (via close contact)  Dose #2 Other, specify _____ <hr/>  Dose #3 DOT by study staff  Dose #3 Self-reported self-administration  Dose #3 Self-administered (reported by someone other than the subject)  Dose #3 Reminded patient to take drug  Dose #3 Indirectly reminded patient to take drug (via close contact)  Dose #3 Other, specify _____	
Rx #3etc.			 Dose #2 DOT by study staff  Dose #2 Self-reported self-administration  Dose #2 Self-administered (reported by someone other than the subject)  Dose #2 Reminded patient to take drug  Dose #2 Indirectly reminded patient to take drug (via close contact)  Dose #2 Other, specify _____ <hr/>  Dose #3 DOT by study staff  Dose #3 Self-reported self-administration  Dose #3 Self-administered (reported by someone other than the subject)  Dose #3 Reminded patient to take drug  Dose #3 Indirectly reminded patient to take drug (via close contact)  Dose #3 Other, specify _____ Check one:  DOT by study staff  Self-reported self-administration  Self-administered (reported by someone other than the subject)  Reminded patient to take drug  Indirectly reminded patient to take drug (via close contact)  Other, specify _____	

For return visits for DOT, allow editing of above table for all individuals.

25. Pill count

Date of pill count	Regimen administered	Is your medication packaging still available?	IF blister pack available, count number of pills remaining	IF blister pack not available, Ask: Approximately how many pills did you take?	Other comments
DD/MM/YY	automatically generated per 22a	 yes  no	half tabs  1  2  3 full tabs (120/20 or 320/40)  0  1  2  3  4  5  6  7  8  9	half tabs  1  2  3 full tabs (120/20 or 320/40)  0  1  2  3  4  5  6  7  8  9	

For return visits for pill count, allow editing of above table for all individuals.

26. Ask: Have you experienced any potential side effects from the medication?

Yes No

26a If YES, specify:

- cough
- fever
- headache
- lack of energy
- abdominal pain
- pale complexion or pallor
- yellow discoloration of skin or eyes (jaundice)
- weakness
- joint pain
- dark urine
- nausea
- vomiting
- diarrhea
- chest pain
- heart palpitations
- other (specify _____)

If YES, complete Appendix S. **Adverse drug reaction (ADR) Report Form**

27. Please explain all measures taken to alleviate these adverse reactions related to the drug

28. Other comments _____

Thank you for our participation in this study.

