4.4 Target Areas

The Target Area will be defined for TPE localities as all individuals residing within 200m of an index case that is detected in passive surveillance and resides in a TPE study locality, with individuals residing immediately beyond 200m included if a minimum of 30 individuals are not enrolled within 200m. This Target Area size was selected based on the existing RACD data whereby the mean number of individuals screened per index case was 32.

The Target Area will be defined for RACD localities as all individuals residing within 500m of an index case that is detected in passive surveillance and resides in a RACD locality. The malaria surveillance team will be trained to focus on maximizing coverage within the immediate 200m radius around the index case. This Target Area size was selected based on the current RACD policy in Swaziland.

Based on collected data on missing individuals, the estimated total number of individuals residing within 200m of an index case is 53. Thus, coverage to date for RACD has been 60%. However return visits do not typically occur at off hours (mornings and evenings). Moving forward, at least one return visit must occur during off-hours to ensure better capture and to maximize the sample size.

If a subsequent index case is reported in a target area (identified either through health facilities or RACD (all secondary cases identified in RACD become index cases)), the RACD intervention will not be repeated within 5 weeks (per current national policy). For the TPE arm, the intervention will not be repeated within 8 weeks or more than twice within the past year (DP drug insert recommends no repeat course within 8 weeks, and no more than 2 courses within one year).

Target Areas that reside on the border between two localities that were randomized to different arms will receive the intervention according to the locality randomization of the index case. For outcome measures, some contamination of the intervention arm's effect may occur if a neighboring locality is randomized to a different intervention. In the analysis we will adjust for distance from an index case for whom the surrounding area received TPE intervention. It will not be necessary to adjust for distance from an area where RACD was conducted because RACD is the current standard of care in all receptive areas of the country.

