TPE intervention	
 • Non-index case, and • Resided or spent at least one night in the Target Area in the past 5 weeks. 	
 • Target Area overlaps with prior Target Area that received the TPE intervention within the past 8 weeks, and • For DP specifically (though still eligible for interview): 
 — Temperature $\geq 38.0^{\circ}\text{C}$, report of fever in the past 48 hours, or other illness (will be referred to the nearest health facility for further evaluation) — Pregnancy, breastfeeding, and women who have had menarche but no menses in the past 4 weeks — Children <9 months of age or <7 kg — Known allergy or history of adverse reaction to DP — Already taken 2 courses of DP in the past year or taken 1 course within the past 2 months — Moderate or severe renal or hepatic insufficiency — Currently with severe malaria — Family history of sudden death or of congenital prolongation of the QTc interval. — Known congenital prolongation of the QTc-interval or any clinical condition known to prolong the QTc interval. — History of symptomatic cardiac arrhythmias or with clinically relevant bradycardia. Any predisposing cardiac conditions for arrhythmia such as severe hypertension, left ventricular hypertrophy (including hypertrophic cardiomyopathy) or congestive cardiac failure accompanied by reduced left ventricle ejection fraction. — Electrolyte disturbances, particularly hypokalaemia, hypocalcaemia or hypomagnesaemia (including vomiting in child) — Recent treatment with medicinal products known to prolong the QTc interval that may still be circulating at the time that DP is commenced (e.g. mefloquine, halofantrine, lumefantrine, chloroquine, quinine and other antimalarial agents)
Pill count	
 • Resides in the first Target Area to receive the intervention for each locality during each transmission season, and • Received antimalarial drugs through the TPE intervention. 	
 • Resides in a locality randomized to the RACD arm.
Acceptability Assessment	
 • Received the TPE intervention, or • Member of surveillance team in both RACD and TPE arms. 	
 • < 18 years of age.

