If an individual cannot safely be given DP, that individual will not be given medication for presumptive treatment. Pregnant women and breastfeeding women will be excluded. All girls ≥ 10 years of age will also be asked about menses. Those who have had menarche but have not menstruated in the past 4 weeks will also be excluded. Infants < 9 months of age or < 7 kg will also be excluded. For infants and children unable to take tablets, drugs will be crushed, mixed with water and administered as a suspension. No more than two courses of DP may be given within a 12-month period. Additionally, a second course of DP should not be given within 2 months after the first course due to the long elimination half-life of piperazine. Other contraindications include: severe malaria, young children who vomit (electrolyte disturbances can increase QTc), heart problems or rhythm disturbances, kidney or hepatic insufficiency, recent treatment with certain medications (antiarrhythmics, neuroleptics, antibiotics, non-sedating antihistamines, antimalarial agents, and others (cisapride, droperidol, domperidone, bepridil, dephemanil, probucol, levomethadyl, methadone, vinca alkaloids, and arsenic trioxide).

Individuals who cannot safely be given DP will be tested by RDT using the *Pf*-specific First Response RDT during the intervention visit. At the time that blood is collected for RDT testing, the same finger prick will be used to generate a slide and dried blood spot. Four spots of blood will be collected for each DBS. A second finger prick will be used to collect microtainer blood samples from RDT-positive individuals. Subjects testing positive by RDT will be referred to the closest health facility for treatment with a drug that is safe for them according to national policy.

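### The two-course annual DP limit is checked at dosing by recall only, and item 52 and Table 3's overlap exclusion carry just the 8-week half of the area rule

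*Combined protocol and SAP*

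**What the plan says.** **The limit.** Section 7.3 states it per person: "No more than two courses of DP may be given within a 12-month period". Table 3 repeats it as a personal exclusion from DP, alongside one course in the past 2 months. Section 4.4 states it per area and cites the drug insert: "For the TPE arm, the intervention will not be repeated within 8 weeks or more than twice within the past year".

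**The area-level forms.** Table 3's area exclusion for TPE reads "Target Area overlaps with prior Target Area that received the TPE intervention within the past 8 weeks". It has no annual count. Appendix C item 52, where supervisors record the planned response, offers one reason for not planning TPE in a TPE locality: TPE already completed in the past 8 weeks.

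**The dosing form.** Appendix K question 15 asks "Have you already taken 2 courses of DP in the past year", and question 16 asks about the last 2 months. Both offer *Yes*, *No* and *Don't know*. The stated rule is "Subject is eligible to receive medication if they weigh at least 7kg and answered 'No' to questions 10-19", together with not taking a listed medicine. Question 22 then says "Tablet to automatically say Yes or No for eligibility of individual to receive medication based on responses above and criteria provided", with the options disabled so that the agent cannot change them.

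**Other information the trial holds.** Appendix J asks each household whether, how often and when it took part in TPE before. Appendix K is completed under a personal barcode and records dose 1. For question 13 (age) the form says "Tablet should automatically complete this question based on date of birth, select an option and not allow Agent to make changes". The end-line household form (Appendix O) is pre-filled from previous visits.

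**The concern.** The plan sets a safety limit with two halves: at least 8 weeks between rounds, and no more than two in a year. Only the first half reaches the form on which supervisors decide whether to send a team, and only the first half is in the overlap exclusion. The second half is left to a question that asks people, or guardians answering for children, to count courses of a named drug over a year. The tablet locks its decision on that answer. Nothing in the stated rule brings in the Appendix J dates or earlier dose-1 records.

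At stake is a third DP course within a year for a person the plan means to exclude.

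**Working it through.** **1. Where each half of the limit appears**

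| Place | 8-week or 2-month limit | Two-per-year limit |
|---|---|---|
| Section 4.4 (area) | yes | yes |
| Table 3, overlap exclusion (area) | yes | no |
| Appendix C item 52 (area) | yes | no |
| Section 7.3 and Table 3 (person) | yes | yes |
| Appendix K (person) | question 16, by answer | question 15, by answer |

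**2. Does the 8-week check imply the annual one?** No. Three rounds need two gaps of 8 weeks: 2 × 8 = 16 weeks, well inside a year. An 8-week check alone would allow rounds at weeks 0, 8, 16, 24, 32, 40 and 48, which is 7 in 52 weeks against a limit of 2. That is what the form check alone permits, not a forecast.

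**3. Overlapping areas.** Two 200 m areas can overlap when their index cases are up to 200 + 200 = 400 m apart. If one area was extended to the 500 m cap in section 6.2, the distance is 200 + 500 = 700 m. Take rounds in area A, then overlapping area B, then A again, each more than 8 weeks apart. A has two rounds and B has one, so neither exceeds section 4.4's count, yet residents of the overlap meet three rounds. The Neighborhood ID does not count these: Appendix J reuses it only within 200 m, and Appendix G issues one per episode. For such residents the person-level check has to work.

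**4. What question 22 does with each answer to question 15**, all else being eligible:
- *Yes*: not eligible.
- *Don't know*: not eligible, because the rule requires *No*.
- Correct *No*: eligible, as intended.
- Wrong *No*: eligible, whatever earlier records show.

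The gap is the last line only. The numbering in the eligibility note looks one off (weight is question 10, and the medicines are under question 21), but questions 15 and 16 fall in the range either way.

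**5. Scale**
- Repeat encounters: section 14.3 gives 66 TPE index cases and 1782 individuals treated. With 30 people per area and the 10% repeats of section 14.1, 66 × 30 = 1980 and 1980 × 0.9 = 1782, which reproduces the plan's figure. Implied repeats are 1980 − 1782 = 198. The 10% comes from RACD data (500 m radius, 5-week rule), so it may be too high for TPE.
- Index cases per TPE locality with any case, using the 22 localities of section 14.1's adherence paragraph: 66 / 22 = 3 over two seasons, or 1.5 a year.
- The same, using 63 of 77 localities with a case and 39 TPE localities: 39 × 63 / 77 = 31.9, about 32; 66 / 32 = 2.1 over two seasons, or about 1 a year.
- Clustering: Table 2 covers 31 months (2.58 years), so more than two cases a year means more than 2 × 2.58 = 5.2, that is, at least 6. Sixteen of the 77 localities reach this, across both arms. Their populations run from 890 to 9,015, whereas section 4.4 says "the estimated total number of individuals residing within 200m of an index case is 53". The counts show where rounds could recur, not that they recur around the same homes.

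**The case against.** The strongest reply is that the limit is already in the form that decides dosing. Question 15 states it, question 22 locks on it, and an unsure person gets no drug. Interview is the plan's declared way of screening for DP, and pregnancy, allergy, heart disease and medicines are also taken by answer. Section 4.4 binds supervisors whether or not item 52 has a box, and the form has a comments field. Staff hold the Appendix J dates at the same visit. Section 13.1 promises SOPs for all activities; neither they nor the tablet specification is in the documents, and they may close the gap. A third course also needs a long chain: three suitably spaced rounds in a year, a person present and eligible at each, and a wrong denial of two courses whose first doses were to be directly observed.

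Most of this stands, and it keeps the point small. It does not remove it. Prior DP given by the trial differs from the other interview items because the trial holds the record. The comparison with question 13 is imperfect, since date of birth is collected at the same visit while dose history must be synced and matched. Appendix O's pre-fill is the closer precedent.

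A reader might infer that the annual limit is missing at dosing, that the 198 repeats are excess courses, or that the 16 busier localities would produce third courses. The documents support none of these. Question 15 enforces the limit, most repeats would be permitted second courses, and the 16 are locality counts covering both arms.

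**Conclusion.** The point holds as a cheap improvement to a safety check. The area-level forms carry half of section 4.4's rule, and the person-level check fails only on a confident wrong *No*. Third courses are probably rare: about 1 to 1.5 index cases per TPE locality with any case per year is below the level at which the limit usually binds, so exposure is confined to places where cases cluster. The number of third courses cannot be derived.

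Likely harm from one extra course is small. Section 17.3 cites a schoolchildren trial in which DP given as often as monthly raised no safety concern. No effect on the primary outcome or the analysis follows.

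The conclusion assumes that *Don't know* is handled as the rule literally reads and that the unseen SOPs and tablet specification add no record check.

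**What to change.** 1. Add to Appendix C item 52 a reason for not planning TPE: already given twice in the past 12 months, counting overlapping and extended areas. Where the overlap is partial, use it as a prompt to check people one by one, so that residents with fewer than two courses are still offered DP.
2. Carry each person's barcode forward at repeat rounds and have the tablet pre-fill or cross-check Appendix K questions 15 and 16 from barcode-linked dose-1 records. Where no record matches, show the Appendix J dates beside those questions. They are household dates and name no drug, so they should prompt a check rather than exclude automatically.
3. Keep the spoken question for DP taken outside the trial and for unmatched people, and state that *Don't know* means not eligible.

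The cost is one form box, tablet programming and syncing of earlier records before repeat visits. Some matches will be imperfect; for those the Appendix J dates and the spoken answer stand. The exclusion rule and the analysis do not change.
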